### 16.2 Automatic functionalities (Part 2)

Due to the fact that echocardiography is prone to considerable inter- and intra-observer variability, it was important to perform comparison of the automatic measurements using data from multiple board certified cardiologists. The first three cardiologists established the acceptable intra- and inter-observer variation ranges while the fourth cardiologist and Ligence Heart were used as independent raters with accuracy calculated as the number of times measurements fell within acceptable variation range in the selected studies. Non-inferiority of automatic measurements accuracy to a cardiologist was established by conducting the t-test and assuring p-values are  $> 0.05$  which proves that any differences are non-significant. All of the measurements passed the required performance threshold, and for 7 out of 21 automatic measurements, both Ligence Heart and FC had full agreement with the ORG.

Conversely, Ligence Heart automatic functionalities did not return a value for at least one study in 11 measurements, however, there was a sufficient number of studies for all measurements where automatic analysis value was returned to ensure statistical power. The reason for no value being returned in a particular study has to do with the automatic predictions not passing quality thresholds which are employed in each step of the automatic functionalities (classification, cardiac phase or cycle detection and measurement prediction confidence). This ensures that a lower number of false values is provided to the user of the medical device and serves as a safety mechanism by reducing the number of potential false positive findings.

**Supplementary figure 1** provides insight into difficulty of performing different measurements. The measurement that has the highest variability and the lowest correlation coefficients between all raters is LVPWd, most likely due to the fact that the inner border of the left ventricular posterior wall is difficult to visualize precisely in a parasternal long axis view. It is worth mentioning that measuring LVPWd is difficult not only for an automated system but for human operators as well. Looking at individual measurement prediction in **Supplementary figure 2** we can observe that LVESV2A has the highest difference between FC and Ligence Heart predictions, however both operators fall within ranges established by the ORG measurements. It is important that variation arises due to multiple factors as the end result depends on multiple steps: selecting the proper echocardiographic video, selecting the right frame in the cardiac cycle and performing the right annotations. Two different operators might make the same measurement in different echocardiographic videos belonging to the same view and because of that they may end up with different results. Different operators can also choose different cardiac cycles and different frames for making the same measurement. In some cases, there might be no single correct answer due to the factors mentioned before and the only way to establish true values would be to use some other imaging method, which is not always feasible. This explains some of the mechanisms behind the variability observed in echocardiography and further shows the need to use data from multiple raters in establishing a benchmark.

It is worth noting that Ligence Heart is the first and only medical device software to our knowledge that can automatically perform a number of linear measurements: AoA, AoS, STJ, AAo, LAD, RVOTPD, RVB, RVM and RAMAD. Additionally, our results are validated using an end-to-end approach where the automated system has to perform echocardiographic view recognition, cycle detection and measure the relevant structure all

UAB Ligence	Clinical Investigation Report	2021-04-09
		Rev: 1.0

at once. In contrast, machine learning in echocardiography publications often only describe the accuracy of a single isolated task, e.g. classification or segmentation and provide metrics that might not necessarily translate well into clinical practice. The literature review shows that even though several studies were validated in multi-centre clinical trials, nevertheless they were only validated on isolated tasks. For example, ML models were shown to be faster and more repeatable for quantification of LVEF (27–29). ML model for quantification of RVEF showed good agreement with cardiac magnetic resonance imaging (30). Automated left ventricle volume quantification did not significantly deviate from the manual method (31). The clinical practice, however, requires more measurements to be performed, rather than only LVEF, RVEF and left ventricular volumes, for a holistic evaluation of a patient.

The automatic functionalities additionally offer the advantage of reproducibility in re-analysis of the same echocardiographic studies. Even though deep neural networks used in Ligence Heart can be considerably complex, they will produce identical output given the same input. In our analysis, we have shown that there is considerable intra-observer variability which can be reduced by using an automated system. The benefits of automated systems for reduced intra- and inter- observer variability are shown by the research as well. A study by Asch evaluated a ML model for detection of reduced LVEF and showed higher consistency, sensitivity, and specificity for detection of reduced LVEF than human operators did, another study by Myhr found that automated LVEF measurements show smaller intra- and inter-operator variability than manual methods do (27,32).

Finally, the time taken by an automated system to perform the same measurements is generally shorter compared to a human operator. It may vary based on the hardware being used. The literature supports the claim that automated methods perform quicker than manual ones as it was shown by Myhr where acquisition and analysis for calculating LVEF for an automated system was  $94 \pm 23$  seconds whereas for a manual method it was  $115 \pm 15$  seconds (32). In our case we used an upper-mid level consumer grade NVIDIA 2080 RTX GPU, which is not beyond what is reasonably available to a healthcare organization.

Overall, we have shown that 1) the automatic functionalities of Ligence Heart have accuracy that is non-inferior to a cardiologist; 2) Ligence Heart produces the same output across two runs on the same echocardiographic studies and has lower intra-rater variability than human operators; 3) Ligence Heart performs automated measurements faster than a human operator.

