#### 4.16 Anticipated Risks

The device under study has undergone risk assessment, in accordance with International Standards Organization (ISO) 14971, and risks have been mitigated to levels as low as reasonably possible (ALARP).

Medical software does not have direct contact with subjects and no additional direct clinical procedures will be conducted for the clinical investigation. Therefore, no harm to the subjects' health is possible during the clinical investigation.

The personal data of the subjects will be processed and stored in the same way as other personal medical information: the researchers undertake to provide the client only with depersonalized (anonymous) information collected during the biomedical research.

Risk management for the medical software Ligence Heart is performed in accordance with ISO 14971:2012.

The following risks that have been identified as relevant for the clinical investigation:

- Cybersecurity breach (R-1);

The risks that have been identified as irrelevant for the clinical investigation, because they are associated with direct management and decision making of the patient's care during regular clinical practice, and during clinical investigation no direct decision making on the further subject clinical management will take place:

- Bug in the code (R-2)
- Software failure during the login and/or study selection process (R-3)
- Failure of the software to save the work progress (R-4)
- Errors of the functions that allow manipulation of the images (such as contrast changing, zooming, adding (annotations etc.) due to bugs (R-5)
- Automatic analysis of inadequate quality echocardiography images (R-6)
- Failure of 3rd party software components (R-6)
- The cloud server is unreachable (R-7)
- Incorrectly configured user's rights (R-8)
- Hardware does not have sufficient resources to run the software adequately (R-9)
- User runs Ligence Heart on incompatible software/operating system (R-10)
- Errors in the communication of the software with the hospital's information system (R-11)
- Erroneous performance of annotations/other aspects of echocardiography exam and approval of the final results by the user (R-12)
- Poor user interface design (R-13)
- Newly released software update is not validated correctly (R-14)

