# 15 Investigation Results

## 15.1 Demographic data

A total of 58 persons from a single center in Lithuania referred to 2D transthoracic echocardiography (TTE) in non-emergency setting were enrolled in the study retrospectively. Among the participants, 100% were Caucasian, 50.0% were female. The mean LVEF was  $50.81 \pm 9.77\%$ , with 13.79% of the participants having LVEF < 50%. The median age was 62.0 years. All participants had sinus rhythm at the time of performing TTE (Table 1a and 1b).

**Table 1a.** Main parameters of the study cohort.

	Mean	± SD
Age (years)	62.05	14.92
Weight (kg)	83.17	14.25
Height (cm)	172.57	10.36
Body surface area	1.99	0.21
Ejection Fraction (%)	50.81	9.85

**Table 1b.** Main descriptive statistics.

	N	(%)
Females	29	50.00
History of Heart Failure	29	50.00
History of Myocardial Infarction	11	18.97
History of Percutaneous Coronary Intervention	14	24.14
History of Coronary Artery Bypass Graft	4	6.90

UAB Ligence	Clinical Investigation Report	2021-04-09
		Rev: 1.0

History of Arterial Hypertension	1	1.72
History of Valvular Heart Disease	43	74.14
History of Coronary Heart Disease	14	24.14
History of Cardiomyopathy	3	5.17
Implantable Device (Pacemaker or Defibrillator)	3	5.17

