## 15.2 Accuracy of automatic measurements (Part 2)

In order to establish the baseline inter- and intra-observer variability, the original rater group (ORG) consisting of three board certified cardiologists analyzed 58 2D TTE studies, repeating the measurements twice. This generated six values for each measurement in each study. The new rater group (NRG) consisting of a fourth cardiologist (FC) and Ligence Heart performed measurements in the same 58 studies. NRG performance was evaluated by calculating the number of measurements of each type that were in the limits of variation. FC was used as the performance benchmark for Ligence Heart.

There was no significant difference in variation between Ligence Heart and FC ( $p > 0.05$ ) and Ligence Heart had non-inferior accuracy to FC for all automatic measurements (**Table 3**). The lowest number of studies in agreement with ORG was 93.1% in RAA and 94.55% in RVM for Ligence Heart and FC, respectively. For AoS, STJ, IVSd, LVEDD, LVESD, LVESV4A and RVOTPD both FC and Ligence Heart were in agreement with ORG for 100% of studies. Ligence Heart discarded 2-4 studies in RAMAD, LAV4A, LVEDV4A, LVESV4A, LVEDV2A, LVESV2A, RVEDA and RVESA due to insufficient quality scores of automatic predictions (**Table 3**). Ligence Heart confidence interval for the number of studies in agreement with ORG intersected FC for all automatic measurements (**Figure 1**) and comparing each measurement between FC and Ligence Heart yielded a median Pearson correlation R 0.74 (IQR 0.59-0.83) (**Figure 2**).

Comparison of correlation between all raters and NRG measurement relation to ORG measurements is visualized in **Supplementary figures 1 and 2**, respectively.

**Table 3.** Comparison of Ligence Heart and cardiologist agreement with original rater group.

Measurement	Ligence Heart studies in agreement with ORG (95% CI)	FC studies in agreement with ORG (95% CI)	P-value*	N studies	N studies not passing confidence filter in Ligence Heart	Pass
RAMAD	96.3 ± 5.03	98.15 ± 3.59	0.56	54	4	Yes
AoA	98.28 ± 3.35	98.28 ± 3.35	1	58	0	Yes
AoS	100.0 ± 0.0	100.0 ± 0.0		58	0	Yes
STJ	100.0 ± 0.0	100.0 ± 0.0		58	0	Yes
AAo	98.28 ± 3.35	100.0 ± 0.0	0.32	58	0	Yes
LAD	94.83 ± 5.7	100.0 ± 0.0	0.08	58	0	Yes
LAV4A	98.21 ± 3.47	94.64 ± 5.9	0.31	56	2	Yes
IVSd	100.0 ± 0.0	100.0 ± 0.0		58	0	Yes
LVPWd	96.55 ± 4.7	100.0 ± 0.0	0.16	58	0	Yes
LVEDD	100.0 ± 0.0	100.0 ± 0.0		58	0	Yes
LVESD	100.0 ± 0.0	100.0 ± 0.0		58	0	Yes
LVEDV4A	98.21 ± 3.47	100.0 ± 0.0	0.32	56	2	Yes

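### Section 16.2 calls the quality thresholds a safety mechanism, but no agreement result is reported for the 34 withheld values, and section 15.2 contradicts itself on RAA and on which measurements were filtered

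*Protocol*

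**What the plan says.** Section 15.1 reports the cohort: "A total of 58 persons from a single center in Lithuania". Section 15.2 compares Ligence Heart and a fourth cardiologist with an original rater group (ORG) of three cardiologists. It counts the studies in which each falls within the ORG limits of variation.

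On the filter, the text of 15.2 states: "Ligence Heart discarded 2-4 studies in RAMAD, LAV4A, LVEDV4A, LVESV4A, LVEDV2A, LVESV2A, RVEDA and RVESA". That is eight measurements. Section 16.2 instead says that the automatic functions "did not return a value for at least one study in 11 measurements", and Table 3 also has 11 rows with withheld studies. According to 16.2 the thresholds act at several steps: "classification, cardiac phase or cycle detection and measurement prediction confidence". It then draws the conclusion at issue: "This ensures that a lower number of false values is provided to the user of the medical device and serves as a safety mechanism".

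On RAA, the text of 15.2 says: "The lowest number of studies in agreement with ORG was 93.1% in RAA" (for Ligence Heart). The RAA row of Table 3 gives 94.44 ± 6.11, with N = 54 and 4 studies not passing the filter.

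**The concern.** Calling a filter a safety mechanism says something about discrimination: the values it holds back should be wrong more often than the values it lets through. Showing that requires the accuracy of the withheld outputs, or a comparison with and without the filter. Section 12.5.2 plans neither and section 15 reports neither. Table 3 gives agreement for returned values only, and the fourth cardiologist's percentages use the same reduced denominators.

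The two mismatches in 15.2 make this harder to judge. A reader cannot tell whether the RAA agreement quoted in the text was obtained before or after filtering. RAA is the weakest Ligence Heart measurement in the report, yet the text does not list it as filtered. At stake are a safety statement in the conclusions of a pre-market report and one of its accuracy figures.

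**Working it through.** **Inputs.** Percentages, N and withheld counts come from Table 3 (section 15.2). The 58 studies come from section 15.1, and the 93.1% from the text of 15.2.

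**1. Reproduce the Table 3 figure for RAA.** 51/54 = 94.44%. The Wald half-width is 1.96 × √(0.9444 × 0.0556 / 54) = 6.11 points, as stated. A two-sample t-test on 0/1 outcomes, 51/54 against 53/54 for the fourth cardiologist, gives p = 0.313 (stated 0.31). The table row is internally consistent.

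**2. Test the text figure.** Over all whole counts with N from 50 to 58, 93.1% arises only as 54/58, whose half-width would be 6.52. It does not fit the table row. The same sentence gives the fourth cardiologist's lowest figure as 94.55% in RVM, which is 52/55 and so a filtered denominator. The sentence therefore mixes bases or contains an error. RAA remains the lowest Ligence Heart result on either figure, since the next lowest is LAD at 94.83%.

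**3. Count the withheld values.** Every Ligence Heart row of Table 3 back-solves to a whole count, and N plus withheld is 58 in each row. The last column takes all withheld values as outside and then all as inside the limits. It assumes that a value exists for each.

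| Measurement | Returned | In agreement | Outside | Withheld | Possible unfiltered agreement |
|---|---|---|---|---|---|
| RAMAD | 54 | 52 | 2 | 4 | 89.7–96.6% |
| LAV4A | 56 | 55 | 1 | 2 | 94.8–98.3% |
| LVEDV4A | 56 | 55 | 1 | 2 | 94.8–98.3% |
| LVESV4A | 56 | 56 | 0 | 2 | 96.6–100% |
| LVEDV2A | 54 | 52 | 2 | 4 | 89.7–96.6% |
| LVESV2A | 54 | 52 | 2 | 4 | 89.7–96.6% |
| RAA | 54 | 51 | 3 | 4 | 87.9–94.8% |
| RVB | 55 | 54 | 1 | 3 | 93.1–98.3% |
| RVM | 55 | 55 | 0 | 3 | 94.8–100% |
| RVEDA | 55 | 54 | 1 | 3 | 93.1–98.3% |
| RVESA | 55 | 54 | 1 | 3 | 93.1–98.3% |
| Total | 604 | 590 | 14 | 34 | |

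There are 11 rows. The eight names in the text omit RAA, RVB and RVM. The share withheld is 34 / (21 × 58) = 34/1,218 = 2.8%.

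**4. What the claim would need.** Among returned values in these 11 measurements, 14/604 = 2.3% were outside the limits. If withheld values were no worse, 34 × 14/604 = 0.79 of them would be expected outside. The actual number is not reported. With 0 outside, the filter removed no false value. With 34 outside, it removed every one of them correctly. The unfiltered out-of-limit rate in these measurements could be anywhere from 14/638 = 2.2% to 48/638 = 7.5%.

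**The case against.** **The sentence claims only a lower count of false values, and withholding outputs cannot raise a count.** The second part is true, but the count may also stay the same: with none of the 34 outside the limits it remains 14. Withholding 34 values at random would also be expected to remove 0.79 false ones. A lower count alone is therefore no evidence of a safety function.

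**No endpoint depends on it, and a clinician must approve every automatic result.** Both parts stand. None of the hypotheses in 12.1 and no pass verdict in Table 3 turns on the filter's discrimination. Sections 4.3, 4.4 and 4.11 require review of automatic results. This limits the weight of the point but does not supply the missing evidence.

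**Some withheld cases may have no value to score.** This stands, because the thresholds also act at view classification and cycle detection. The rerun has to allow for it.

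**A reader might infer that the filter removes mostly correct values.** If 93.1% is the unfiltered RAA result, the 4 withheld values split into 54 − 51 = 3 in agreement and 1 not. The documents do not support going further. 54/58 is also exactly the share of RAA studies that returned a value, so the figure may be a mix-up. Even on the unfiltered reading, withheld values were worse (1/4 against 3/54) and the false rate falls from 4/58 = 6.9% to 3/54 = 5.6%, which weakly favours the filter. Four values decide nothing: the exact 95% interval for 3/4 is 19% to 99%, and Fisher p for 1/4 against 3/54 is 0.25.

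**Conclusion.** The point holds in a limited form. The benefit of the thresholds is asserted in 16.2 without any reported agreement result for the 34 withheld values. Section 15.2 carries two internal contradictions: RAA at 93.1% against 94.44%, and 8 filtered measurements against 11. The contradictions need no assumption beyond whole-number counts. The range of 0 to 34 assumes that each withheld case has a value.

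Three other readings go too far:

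- That the withheld outputs were never scored. The document shows only that no such result is reported, and an unfiltered 54/58 for RAA would mean that those outputs had been scored.
- That 16.2 claims control of the risk listed in 4.16 as "Automatic analysis of inadequate quality echocardiography images (R-6", or that the risk-benefit conclusion in 16.3 rests on the filter. Section 16.2 names neither the risk nor image quality, and describes thresholds on predictions. Section 16.3 cites Table 5 and the expected performance in 4.2, not the filter.
- That 14/604 = 2.3% outside in the filtered measurements against 7/580 = 1.2% in the other ten says something about the filter. These are different measurements, not the filter on and off.

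**What to change.** 1. In 15.2, reconcile the RAA figure with Table 3 and state its numerator and denominator, and whether it is before or after filtering. Use one basis for every figure in that sentence.
2. In 15.2, correct the list of filtered measurements to the 11 in Table 3 by adding RAA, RVB and RVM.
3. Rerun the withheld cases with thresholds off, in the same software build, and score them against the same ORG limits. Report out-of-limit counts and rates for withheld and for returned values, with exact intervals, and how many withheld values were acceptable. Where no value exists, state the step that failed. Expect wide intervals: even 0 of 34 outside has an exact two-sided 95% upper limit of 1 − 0.025^(1/34) = 10.3%, and several withheld values may come from one study.
4. Unless withheld values prove worse, replace the conclusion in 16.2 with wording such as: the thresholds are intended to limit unreliable values shown to the user; whether withheld values were less accurate than returned ones was not tested in this investigation.

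The cost is two text corrections, a rerun of at most 34 outputs and a short table. The ORG measured all 58 studies and section 15.3 says that output is fully determined by input, so no new reading is needed and the rerun is reproducible. The downside is that the safety statement may have to be withdrawn.

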### 16.3 Assessment of risks and clinical benefits

No additional risks have been identified and included in the Risk management file during this Clinical Investigation. As it has been previously summarized in **Table 5** no adverse events occurred during the trial and device deficiencies have been reported. This information further proves the safety of the device under investigation.

Considering that Ligence Heart has been proven to meet all the expected performance requirements (described in section 4.2 of this document) that are based on the definition of the State of the Art (described in section 4.12 of this document), it can be firmly concluded that it provides the defined clinical benefits while minimizing the risks.

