# **5 Study Objectives and Endpoints**

## **5.1 Purpose of the Study**

The purpose of this study is to evaluate the safety and performance of the manual and automatic functionalities of medical device software Ligence Heart comparing them to the state-of-the-art alternatives.

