### 10.1 Anticipated Adverse Events

No foreseen risks that could be considered adverse events could results from this study, as no direct contact with the patients will be held and no additional clinical procedures will be performed.

There is always a chance of unforeseen risks. Throughout the study, the Sponsor will evaluate and update safety information in study documents.

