## 15.4 Summary of Safety

**Table 5.** Summary of Adverse Events.

Adverse events	Occurred events

Serious adverse events (AE):
 
Any untoward medical occurrence, unintended disease or injury, or untoward clinical signs (including abnormal laboratory findings) in subjects, users or other persons, whether or not related to the investigational medical device
 
NOTE 1: This definition includes events related to the investigational medical device or the comparator.
 
NOTE 2: This definition includes events related to the procedures involved.
	0

UAB Ligence	Clinical Investigation Report	2021-04-09
		Rev: 1.0

NOTE 3: For users or other persons, this definition is restricted to events related to investigational medical devices.	

Adverse device effects (ADE)
 
Adverse event related to the use of an investigational medical device
 
NOTE 1: This definition includes adverse events resulting from insufficient or inadequate instructions for use, deployment, implantation, installation, or operation, or any malfunction of the investigational medical device.
 
NOTE 2: This definition includes any event resulting from use error or from intentional misuse of the investigational medical device
	0

Serious Adverse Event (SAE):
 
Adverse event that
 
a) led to death,
 
b) led to serious deterioration in the health of the subject, that either resulted in
 
1) a life-threatening illness or injury, or
 
2) a permanent impairment of a body structure or a body function, or
 
3) in-patient or prolonged hospitalization, or
 
4) medical or surgical intervention to prevent life-threatening illness or injury or permanent impairment to a body structure or a body function,
 
c) led to fetal distress, fetal death or a congenital abnormality or birth defect.
 
NOTE 1: Planned hospitalization for a pre-existing condition, or a procedure required by the CIP, without serious deterioration in health, is not considered a serious adverse event.
	0

Serious Adverse Device Effect (SADE):
 
Adverse device effect that has resulted in any of the consequences characteristic of a Serious Adverse Event
	0

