
Unanticipated Serious Adverse Device Effect (USADE):
 
Serious adverse device effect which by its nature, incidence, severity or outcome has not been identified in the current version of the risk analysis report
 
NOTE: Anticipated serious adverse device effect (ASADE) is an effect which by its nature, incidence, severity or outcome has been identified in the risk analysis report.
	0

Unanticipated Adverse Device Effect (UADE):
 
Any serious adverse effect on health or safety or any life-threatening problem or death caused by, or associated with, a device, if that effect, problem, or death was not previously identified in nature, severity, or degree of incidence in the investigational plan or application, or any other unanticipated serious problem associated with a device that relates to the rights, safety, or welfare of subjects.
	0

Device deficiencies
 
Inadequacy of a medical device with respect to its identity, quality, durability, reliability, safety or performance
 
NOTE: Device deficiencies include malfunctions, use errors, and inadequate labelling
	0

UAB Ligence	Clinical Investigation Report	2021-04-09
		Rev: 1.0

Relevant corrective actions	None Needed
------------------------------------	-------------

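### Section 16.3 treats zero adverse events as proof of device safety, although the design excluded harm to subjects, so the count cannot support a conclusion on patient safety

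*Protocol*

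**What the plan says.** Section 5.1 gives safety as one of two aims: "The purpose of this study is to evaluate the safety and performance of the manual and automatic functionalities". Sections 5.2.2 and 5.3.2 make it an objective and an endpoint, namely the type and number of adverse events, serious adverse events and device issues.

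The document also explains why subjects could not be harmed. Section 4.16 says "Medical software does not have direct contact with subjects and no additional direct clinical procedures will be conducted for the clinical investigation", and concludes that no injury to subjects' "health is possible during the clinical investigation". Section 4.18 repeats this as a consequence of the design. Section 11.4 uses the impossibility of side effects as a ground for waiving consent. Section 10.1 adds "No foreseen risks that could be considered adverse events could results from this study", though its next paragraph allows for unforeseen risks.

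Table 5 in Section 15.4 ("Summary of Adverse Events") shows 0 in every event class. It also shows 0 for device deficiencies, defined there as "Inadequacy of a medical device with respect to its identity, quality, durability, reliability, safety or performance".

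Section 16.3 notes that no additional risks were identified, says that "no adverse events occurred during the trial and device deficiencies have been reported", and concludes: "This information further proves the safety of the device under investigation". The limitations in Section 16.4 do not mention that harm to patients could not have been observed.

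**The concern.** The same fact is used for two purposes. Sections 4.16, 4.18 and 11.4 use the absence of any route to patient harm to show that the study is harmless to its subjects, and that follows. Section 16.3 then uses the resulting zero to show that the device is safe, and that does not follow. An outcome that had to be zero cannot separate a safe device from an unsafe one.

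The risks that matter in use, such as software bugs, automatic analysis of inadequate images and erroneous annotations approved by the user, are listed in Section 4.16 as irrelevant to this investigation because no patient-management decision was taken. The adverse event count therefore says nothing about their consequences for patients. At stake is the conclusion on a stated purpose of a pre-market report for a class IIb device (synopsis and Section 4.5).

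**Working it through.** **The document's own figures.** The safety conclusion rests on 0 events in 58 subjects (Table 5; Section 15.1 for the 58). With per-subject probability of harm p, P(0 events) = (1 − p)^58. The document's premise is p = 0, so P(0 events) = 1. This holds for a safe and for an unsafe device, so the likelihood ratio between them is 1/1 = 1. The zero is reproduced, and it carries no evidence on patient safety.

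The only design figure, N = 54 (Section 12.2), also reproduces. For the within-between interaction, λ = N·f²·m/(1 − ρ) = 54 × 0.0625 × 2/0.4 = 16.875, with 2 and 51 degrees of freedom and α = 0.05. Power is 0.9555. The smallest N reaching 0.95 is 53 (power 0.9518), and 54 is the next multiple of three. That calculation concerns an ANOVA effect and has no bearing on safety.

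**Illustration only: had the 58 been exposed.** Assume, contrary to the design, that device output had guided the care of all 58. The exact upper limit after 0 of 58 is 1 − 0.05^(1/58) = 5.0% (one-sided 95%) or 1 − 0.025^(1/58) = 6.2% (two-sided 95%). A true event rate of 1% would still give no events with probability 0.99^58 = 0.56, and a rate of 2% with probability 0.98^58 = 0.31. Since nobody was exposed, even these limits do not apply.

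**What could have been non-zero.** The definitions in Section 10.2 extend adverse events to users and other persons, and device deficiencies to malfunctions and use errors. Section 4.16 keeps a cybersecurity breach as a relevant risk. These counts were free to vary, so zeros there say something about how the software ran. They say nothing about what happens to a patient managed on its output. As worded, Section 16.3 says that deficiencies were reported, while Table 5 shows 0. A missing negative is the likely explanation, but the two must be reconciled.

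**Error data already in Table 3 (Section 15.2).**
- Returned values: 10 measurements × 58 + 3 × 56 + 4 × 54 + 4 × 55 = 580 + 168 + 216 + 220 = 1184.
- Attempts: 21 × 58 = 1218. Not returned: 1218 − 1184 = 34, or 2.8%.
- Ligence Heart outside the limits, from percentages times N: RAMAD 2, AoA 1, AAo 1, LAD 3, LAV4A 1, LVPWd 2, LVEDV4A 1, LVEDV2A 2, LVESV2A 2, RAA 3, RVB 1, RVEDA 1, RVESA 1. Total 21 of 1184.
- Fourth cardiologist outside the limits: RAMAD 1, AoA 1, LAV4A 3, RAA 1, RVB 1, RVM 3. Total 10 of 1184.

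**Conflicts in those inputs.** The text of Section 15.2 gives RAA agreement for Ligence Heart as 93.1%, which fits 54/58 (4 outside). Table 3 gives 94.44%, which fits 51/54 (3 outside). The text names eight measurements with discarded studies, whose Table 3 counts sum to 4 + 2 + 2 + 2 + 4 + 4 + 3 + 3 = 24. Table 3 shows eleven, adding RAA 4, RVB 3 and RVM 3, which gives 34. Section 16.2 also says eleven, which supports the table.

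**The case against.** The strongest reply is that the safety endpoint is wider than harm to subjects. It includes device issues, and the adverse event definition covers users. Section 10.1 leaves room for unforeseen risks, and Section 4.16 names a cybersecurity breach as relevant. A reader might infer from the argument above that the whole safety endpoint was empty by construction. The documents do not support that. Only harm to subjects' health is excluded by design, and the other zeros carry limited information on software function. This part of the reply stands, but it does not rescue a claim that device safety was proved.

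A reader might also infer that the benefit-risk conclusion closing Section 16.3 is built on the adverse event count. It is not. It expressly cites the performance requirements of Section 4.2, which cover accuracy, reliability, variability and time and include no safety requirement. What remains is that its reference to minimised risks gains no support from zero subject events and should be worded within that limit.

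Finally, a reader might infer that the trial ignored its error data, or that out-of-limit values should become the safety endpoint. Table 3 already reports agreement beside the fourth cardiologist with confidence intervals, and Section 16.2 discusses non-returned values, which it presents as a safety mechanism. A value outside the limits is not a safety event. Section 16.2 accepts that some measurements may have no single correct answer, and Sections 4.3 and 4.4 require a clinician to approve automatic results. Redefining the endpoint once results are known would be unsound.

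**Conclusion.** The point holds in a limited form. On the document's own premise that harm to subjects was impossible, zero subject adverse events among 58 was certain and gives no support to a conclusion on patient safety. The sentence claiming proof should go. Absent deficiencies, user events and security breaches bear on software function only, subject to reconciling Section 16.3 with Table 5.

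Nothing here shows the device to be unsafe, and no accuracy, variability or timing result changes. The counts of 21 and 10 of 1184 are descriptive. They come from 21 measurements on the same 58 studies, so values are clustered and the difference is not evidence of inferiority. They also rest on Table 3 being right where it conflicts with the text of Section 15.2. Following the text instead would add one RAA value outside the limits (22) and cut the non-returns to 24.

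**What to change.** In Section 16.3, delete the sentence claiming proof of safety. State instead that no adverse events were recorded, that the retrospective design could not show patient harm, and that safety in clinical use was not assessed in this investigation. Correct or explain the device-deficiency clause against Table 5. Add the same limitation to Section 16.4, and restrict the closing statement on minimised risks accordingly.

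Optionally, refer in Section 16.3 to the out-of-limit and non-returned values in Table 3, labelled post hoc, descriptive and clustered within 58 studies, and leave the specified safety endpoint as it is. Before doing so, reconcile Table 3 with the text of Section 15.2 on RAA agreement (93.1% against 94.44%) and on the number of measurements with discarded studies (eight against eleven).

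The cost is a few sentences and, if the option is taken, a cross-reference to existing data. The downside is a less favourable safety statement.
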